13. STATISTICAL ANALYSES

Descriptive and position analyses (mean, median, standard deviation, and interquartile range) will be conducted for the description of the quantitative variables. Categorical variables will be described with linear models. Any classification or stratification techniques (multivariate statistics) will be applied to identify participants' profiles. All the statistical analyses will be conducted using the statistical package for the social sciences, Jamovi 2.3.21 software.

14. ETHICAL ASPECTS

This study will be conducted in accordance with the present protocol, with the principles of good clinical practice, according to the ICH Good Clinical Practice standards and the requirements of the Guidelines, with the principles of the Declaration of Helsinki. The study protocol and all other necessary documents will be submitted to the Competent Authorities. Amendments and new versions of the protocol will be promptly shared with the competent Ethics Committee. The present study will be conducted in accordance with the protocol defined by the investigators involved.

Before starting any study procedure, the study protocol and documents will be notified to the Clinical Trial Center and the Ethics Committee of the San Raffaele Hospital in Milan.

 
I.R.C.C.S. Ospedale San Raffaele
	
STUDY PROTOCOL
	
WUIPS Version n. 1 23.08.2023

---	------------------------------	---

15. PARTICIPANT INFORMATION AND CONSENT

All the participants will be invited to voluntarily contribute to the study. The purpose of the study and related procedures will be explained to them. The participants will also be allowed to clarify doubts or uncertainties by asking questions and receiving clear and satisfactory answers. Having read the study information, the participants will have the time to decide whether to proceed with signing the informed consent. Healthcare professionals and administrative workers will agree to a brief privacy policy and electronic release of informed consent (by email) before completing the survey and the questionnaires. For female patients and female caregivers', a paper informed consent will be required to be signed. The decision not to participate in the survey will not affect future nursing care. All participants receive the same care and support from healthcare personnel. Prior to participation in the study, the subjects will receive a copy of the signed and dated written informed consent form.

16. DATA QUALITY, DATABASE MANAGEMENT

The research group will be responsible for data management, data control and quality assurance. The anonymous data will be collected in the eCRF: the data deriving from healthcare professionals and administrative workers will be directly registered in RedCap, while the paper data of patients and caregivers will be manually uploaded.

The data collected will be recorded, processed, managed and archived in paper form and in an automated and computerised form for the sole purposes connected with research, in compliance with Legislative Decree 30/06/2003 n°196 and subsequent authorizations and in compliance with the European regulation n. 679 of 2016. The Principal Investigator will be responsible for data management.

In each hospital center involved in the study, a nurse will be identified as the contact person of the Center, who will be responsible for supervising the appropriate recording of data and compliance with this research protocol.

All data contained in the database specifically set up for the study cannot be attributable to the individual patient: the data are collected anonymously. The patient's personal data are not of interest to the Experimentation in question.

16.1 Data confidentiality and privacy

The privacy of the recruited subjects will be completely guaranteed, and the data will be treated confidentially in the terms prescribed by Italian law in the Legislative Decree 30 June 2003, n. 196, "Code regarding the protection of personal data" (Official Gazette n. 174 of 29 July 2003 – Ordinary Supplement n. 123) and in compliance with the European General Data Protection Regulation n.679 of 2016. The data collected during the study will be kept anonymous and processed for scientific purposes only. They will never be published as individual data but will serve exclusively, in an aggregated way with those of all the other

 
I.R.C.C.S. Ospedale San Raffaele
	
STUDY PROTOCOL
	
WUIPS Version n. 1 23.08.2023

---	------------------------------	---

participants in the study, to produce descriptive analysis results. The investigators ensure that the confidentiality of the participants will be maintained and only an identification number in the register will identify them. All documents will be kept securely and accessible only by the investigators or other authorised personnel. The study will comply with the Italian laws on protecting personal data and the guidelines stipulated on July 24, 2008.

16.2 Data ownership

The ownership of the data relating to the study, its execution and its results belong to the Promoter (DL 17/12/2004). The Coordinating Center will be responsible for data management and storage in compliance with the current regulations (DL 196/2003: "Data Protection Code personal data, June 30, 2003"). The study is promoted by the IRCCS San Raffaele Hospital (Milan), which will also take care of the scientific and operational coordination and which will be responsible for the ownership of the data deriving from the research.

17. DATA PUBLICATION

The research will be made known to the population and to all interested people through communications at conferences, congresses, symposiums, dissemination articles and articles in national and international scientific journals. The research group must authorise and coordinate any studies derived from subgroup analyses. The research group will prepare the study's final report, which will be presented in a meeting. The research group will define the authorship of the works that will be produced in relation to the involvement and work done by the individual. In all the works that will be produced, the promoter of the study must be reported and mentioned in the acknowledgements section.

All publications and/or communications related to the study will be approved in advance by the research group. The transmission or dissemination of global data, through scientific publications and / or presentation in congresses, conferences and seminars, will take place exclusively following the consent of the Promoter Center and the Hospital Centers included in the study after statistical processing of the same and in any case in aggregate and anonymous form.

18. CONSERVATION OF STUDY DOCUMENTS

All information relating to the study participants, the documentation relating to the submission and approval by the EC and the regulatory documentation will be kept by the Principal Investigator in the archive of the IRCCS San Raffaele Hospital (Milan).

19. FINANCIAL ARRANGEMENTS

The study is non-profit. Given the observational nature of the study, insurance coverage is not provided as it is unnecessary.

APPENDIX

UI SURVEY – SCHEDA di RACCOLTA DATI

Gentilissima, nel ringraziarla per aver accettato di contribuire a questa ricerca, la invitiamo a rispondere alle domande di seguito, di natura clinica e socio-demografica, con le quali indaghiamo alcuni fattori che potrebbero essere predisponenti all'insorgenza di una condizione nota come incontinenza urinaria.

1. Indichi il suo anno di nascita:

--	--	--	--

2. Indichi la sua nazionalità:

1. Italiana
 2. Straniera (specificare _____)

3. Indichi la regione di domicilio:

- 1. Lombardia
- 2. Altra regione (specificare _____)

4. Se è domiciliata in Lombardia, indichi la provincia del suo domicilio:

 1. Bergamo	 5. Lecco	 9. Monza
 2. Brescia	 6. Lodi	 10. Pavia
 3. Como	 7. Mantova	 11. Sondrio
 4. Cremona	 8. Milano	 12. Varese

5. Indichi il suo peso in chili:

--	--	--

6. Indichila sua altezza in centimetri

10 cm

7. Indichi il grado massimo di studi raggiunto (scolarità):

- 1. Educazione primaria (elementari, medie)
- 2. Educazione secondaria o avanzata (diploma di istituto professionale, tecnico o liceo, laurea)

8. Soffre o ha mai sofferto di una delle seguenti patologie? (Può indicare anche più di una risposta):

- 1. Insufficienza cardiaca
- 2. Insufficienza renale cronica
- 3. Broncopneumopatia cronico-ostruttiva (BPCO)

- 4. Diabete
- 5. Ipertensione
- 6. Sindrome metabolica
- 7. Prollasso vescicale / vaginale / rettale
- 8. Infezione ricorrente delle vie urinarie
- 9. Sindrome da intestino irritabile
- 10. Stipsi
- 11. Disturbi del sonno
- 12. Depressione
- 13. Patologia neurologica
- 14. Disabilità cognitiva generale
- 14. Altro (specificare: _____)

9. Ha mai subito interventi di chirurgia ginecologica e/o urologica?

- 1. Sì
- 2. No

10. Se alla domanda precedente ha risposto Sì, specifichi quale/i intervento/i ha subito:

11. In quale stato menopausale si definirebbe?

- 1. In pre-menopausa
- 2. A inizio menopausa
- 3. In post-menopausa

12. Ha figli?

- 1. Sì
- 2. No

13. Se alla domanda precedente ha risposto Sì, indichi il numero di figli:

- 1
- 2
- ≥ 3

14. Indichi l'anno di nascita dell'ultimo figlio

--	--	--	--

15. Quanti parto per via vaginale ha avuto?

- 0
- 1
- 2
- ≥ 3

16. Quanti parto cesarei ha avuto?

- 0
- 1
- 2

□ > 3

17. Pratica attività fisica in maniera frequente?

18. Fuma o ha mai fumato?

1. Attuale fumatore 2. Ex fumatore 3. Mai fumatore

19. Se fuma o fumava, quante sigarette al giorno consuma/consumava?

1-5 > 10-20
 > 5-10 > 20

20. Quanti caffè assume in media al giorno?

0 2
 1 3

21. Quanti drinks alcolici assume in media a settimana?

 0	 15-21
 1-7	 ≥ 22
 8-14	

22. Quanta acqua beve in media al giorno?

- 1. Meno di $\frac{1}{2}$ litro
- 2. Tra $\frac{1}{2}$ litro e un litro
- 3. Più di un litro, fino a un litro e $\frac{1}{2}$
- 4. Più di un litro e $\frac{1}{2}$

23. Quante volte al giorno svuota la vescica mediamente?

- 1. Ogni ora o più frequentemente
- 2. Ogni due-tre ore circa
- 3. Ogni quattro ore o meno frequentemente

ICIQ-UI Short Form (Italian)

A molte persone capita, a volte, di avere delle perdite di urina. Stiamo tentando di determinare quante persone abbiano delle perdite di urina e quanto ciò costituisca, per loro, un problema. Le saremmo grati se rispondesse alle seguenti domande facendo riferimento a come si è sentita, in media, nelle ULTIME QUATTRO SETTIMANE.

24. Con quale frequenza le capita di avere delle perdite di urina? (faccia una crocetta su una sola casella)

- 1. Mai
- 2. Una volta la settimana o meno
- 3. Due tre volte la settimana

- 4. Circa una volta al giorno
- 5. Più volte al giorno
- 6. Continuamente

25. Ci piacerebbe sapere qual è, secondo lei, la quantità di urina che perde. Quanta urina le capita di perdere di solito (sia quando indossa una protezione che quando non la indossa)? (faccia una crocetta su una sola casella)

- 1. Per niente
- 2. Una piccola quantità
- 3. Una discreta quantità
- 4. Una notevole quantità

26. In generale, in che misura le perdite di urina hanno interferito con la sua vita quotidiana? La preghiamo di fare un cerchietto attorno ad un numero tra 0 (per niente) e 10 (moltissimo)

0 1 2 3 4 5 6 7 8 9 10

per niente

moltissimo

27. In che occasione le capita di avere delle perdite di urina? (Indichi, tra le seguenti, tutte le situazioni che corrispondono al suo caso)

- 1. Mai – non ho perdite di urina
- 2. Ho perdite di urina prima di riuscire a raggiungere il bagno
- 3. Ho perdite di urina in occasione di colpi di tosse o starnuti
- 4. Ho perdite di urina quando sono addormentata
- 5. Ho perdite di urina quando sono in movimento e durante l'attività fisica
- 6. Ho perdite di urina quando ho finito di urinare e mi sono rivestita
- 7. Ho perdite di urina senza ragioni particolari
- 8. Ho perdite di urina continuamente

Incontinence Impact Questionnaire-7 (Italian)

Le saremmo grati se rispondesse a queste ultime domande, per comprendere l'influenza sulla qualità di vita delle perdite di urina che ha riscontrato.

NOTA BENE: Se non ha mai riscontrato perdite di urina, le chiediamo di apporre una crocetta sul seguente quadratino e di non rispondere alle domande nella tabella. Grazie per la collaborazione.

- Non ho perdite di urina

Se ha riscontrato perdite di urine, queste perdite hanno influenzato...

	Per nulla	Molto poco	Un po'	Molto
28. La sua capacità di fare le faccende domestiche (cucina, pulizie di casa, lavanderia, ecc.)?	0	1	2	3
29. Le sue attività fisiche ricreative, come camminare, nuotare, o fare	0	1	2	3

altro esercizio?				
30. Le sue attività del tempo libero (andare al cinema, concerti, ecc.)?	0	1	2	3
31. La sua capacità di viaggiare in auto o in autobus per più di 30 minuti da casa?	0	1	2	3
32. La sua partecipazione ad attività sociali fuori casa?	0	1	2	3
33. La sua salute emotiva (nervosismo, depressione, ecc.)?	0	1	2	3
34. I suoi sentimenti di frustrazione?	0	1	2	3

Di seguito le poniamo qualche domanda su insorgenza, evoluzione, impatto della patologia e costi da essa derivanti.

NOTA BENE: Se non ha mai riscontrato perdite di urina, le chiediamo di apporre una crocetta sul seguente quadratino e di non rispondere alle domande successive. Grazie per la collaborazione.

Non ho perdite di urina

35. Da quanto tempo ha delle perdite di urina?

- 1. Da 1 anno o meno
- 2. Da 2-5 anni
- 3. Da 6-10 anni
- 4. Da più di 10 anni

36. Le sue perdite di urina hanno influenzato la sua vita sessuale?

- 1. Per nulla
- 2. Molto poco
- 3. Un po'
- 4. Molto

37. Le sue perdite di urina hanno comportato assenteismo o minore produttività sul posto di lavoro?

- 1. No
- 2. Sì, raramente
- 3. Sì, a volte
- 4. Sì, spesso

38. In media, potrebbe fornire una stima della spesa settimanale che sostiene per l'acquisto di prodotti igienici specifici per le perdite di urina (assorbenti o pannolini, salviettine, detergenti intimi specifici, ecc.)?

- 1. Non acquisto alcun prodotto specifico per le perdite di urina
- 2. Spendono meno di 3 euro a settimana
- 3. Spendono fino a 5 euro a settimana

- 4. Spendò tra i 6 e i 10 euro a settimana
- 5. Spendò più di 10 euro a settimana

39. Ha svolto delle visite specialistiche per il problema delle perdite di urina?

- 1. No (perché _____)
- 2. Sì, con un ginecologo / un urologo
- 3. Sì, con un'ostetrica / un infermiere / un fisioterapista
- 4. Sì, con un altro professionista sanitario (specificare _____)

40. Sta seguendo qualche trattamento per risolvere il problema delle perdite di urina?

- 1. Sì (specificare _____)
- 2. No

LA RINGRAZIAMO MOLTO PER AVER RISPOSTO ALLE NOSTRE DOMANDE

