4. OUTCOMES

Primary outcome

- Prevalence of middle-aged women with urinary incontinence.

Secondary outcomes

- Description of UI and related predictors, quality of life, social impact and costs.
- Association between UI and related predictors, quality of life, social impact and costs.

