5. EXPECTED RESULTS

The collection of data and information through this study will aim to:

- a) Understand the percentage of middle-aged women with UI.

 
I.R.C.C.S. Ospedale San Raffaele
	
STUDY PROTOCOL
	
WUIPS Version n. 1 23.08.2023

---	------------------------------	---

- b) Describe the socio-demographic and clinical characteristics of women with UI.
- c) Identify UI predictors.
- d) Describe the quality of life, social impact and costs of women with UI.

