7. INCLUSION/EXCLUSION CRITERIA

7.1 Inclusion criteria

- Female sex
- Middle age (40-65 years old)
- Informed consent signed
- Comprehension of written and spoken Italian language
- Female outpatients intended for any hospital unit (outpatient clinic, day surgery and day hospital patients included) and every female caregiver respecting the previous inclusion criteria, recruited at the central admission and at the private admission of the four hospitals involved
- Female workers (healthcare professionals and administrative personnel) of the four hospitals

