9. DATA COLLECTION

All the data will be collected based on a series of variables which derive from an accurate narrative review of the UI predictors, costs and quality of life of the women affected by the problem (Danforth et al., 2006; Datar et al., 2022; Goren et al., 2014; Harding et al., 2023; Sensoy et al., 2013). These variables are described in Table 1. The obtained information will be gathered in the eCRF, which the investigators will only access during the analyses and synthesis of data.

Table 1 - Outcome and description of the investigated variables

OUTCOME	VARIABLE	DESCRIPTION
UI predictors	Age	The prevalence of UI seems strongly related to the age of the woman and specifically prevalence figures increase with increasing age (Milsom & Gyhagen, 2019)

	Ethnicity	The risk of SUI appears to be lower in black and Asian-American women compared to white women (Danforth et al., 2006; Thom et al., 2006)
	Scholarship	According to some studies (Batmani et al., 2021; Marques et al., 2015), increasing the level of education is an important factor in reducing the incidence of urinary incontinence
	Body Mass Index (BMI)	There is evidence that the prevalence of both UUI and SUI increases proportionately with BMI (Harding et al., 2023)
	Comorbidities	
Lower urinary tract symptoms are associated with multiple comorbid conditions including:
 
 • cardiac failure • chronic renal failure • chronic obstructive pulmonary disease • diabetes • hypertension • metabolic syndrome • pelvic organs prolapse • urinary tract infections • bowel disorders (constipation, irritable bowel syndrome) • sleep disturbances • depression • neurological disease • general cognitive impairment 
(Batmani et al., 2021; Harding et al., 2023; Sensoy et al., 2013; Wang et al., 2010)

	Pelvic or uro-gynecological surgery	Other factors positively associated with SUI include previous pelvic or uro-gynecological surgery (Ellström Engh et al., 2006; Harding et al., 2023)

	Menopause	Menopausal status seems to influence the onset and characteristics of urine leakage (Sensoy et al., 2013; Thangarajah et al., 2020)
	Parity	Pregnancy and childbirth are triggers for SUI (Li et al., 2023; Bortolotti et al., 2000)

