11. NUMBER OF CASES

The population sample cannot be decided accurately in advance. Population studies from numerous countries have reported that the prevalence of UI among all adult women ranged from approximately 5% to 70% worldwide, with most studies reporting a prevalence of UI in the range of 25–45% (Miano et al., 2012; Milsom & Gyhagen, 2019). To date, limited epidemiologic research has been conducted in Italy on this matter. One of the most recent Italian studies was conducted in 2002 and prevalence of UI was found to be 10.2% in a sample of 13365 women older than 40 years (Miano et al., 2012; Parazzini, Lavezzari & Arbitani, 2002).

To define an indicative sample size for our search, reference will be made to the sample considered by two prevalence studies conducted in some specifical Italian districts. The first one proposed telephonic interviews to the population of a big area composed by six cities, including a total of 2.767 women aged ≥ 40 years old (Bortolotti et al., 2000). The second study investigated by questionnaire the prevalence and characteristics of UI in a female sample composed by 2.900 subjects aged between 18 and 49 years living in the urban area of Trieste (Siracusano et al., 2003).

Our study will investigate UI prevalence in middle-aged women (40-65 years old) identified in four hospitals in Northern Italy. The competent Departments were asked for data on the average daily accesses of patients to the hospitals involved and the number of female personnel hired with an age range of 40-65

years. As regards the female personnel between 40 and 65 years old hired at San Raffaele Hospital and San Raffaele Turro Hospital, there are 1.842 employees. The sample will be determined based on the data we will receive from other hospitals.

After this study, we could expand the protocol to include other centers to better evaluate the phenomenon and investigate the prevalence in a larger population.

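### Question 7 reduces education to two levels and puts diploma and degree in one box, so the rising-level rationale in Table 1 cannot be examined

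*Protocol*

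**What the plan says.** Section 9, Table 1, includes schooling among the UI predictors. The reason it gives, from cited studies, is that "increasing the level of education is an important factor in reducing the incidence of urinary incontinence". Predictors serve two stated purposes: expected result (c) in Section 5, "Identify UI predictors", and a secondary outcome in Section 4, "Association between UI and related predictors, quality of life, social impact and costs".

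Education is measured once, in the Appendix: "7. Indichi il grado massimo di studi raggiunto (scolarità". The two answers are "1. Educazione primaria (elementari, medie" and "2. Educazione secondaria o avanzata (diploma di istituto professionale, tecnico o liceo, laurea". None of the other questions asks about schooling, and none asks about occupation.

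Hospital staff are one of the recruited groups (Section 7.1: "Female workers (healthcare professionals and administrative personnel) of the four hospitals"). Section 11 gives a count for two of the four hospitals: "As regards the female personnel between 40 and 65 years old hired at San Raffaele Hospital and San Raffaele Turro Hospital, there are 1.842 employees". Section 8 has staff answer online and patients and caregivers on paper. Section 13 names no coding or trend test for education, and no section gives an education distribution for any group.

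**The concern.** The stated reason for including education concerns rising level, but the item can only separate women who stopped at middle school or earlier from everyone else. Among women with any upper-secondary diploma, those with and without a degree look identical in the data.

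This is a limit of data capture, so no later analysis plan can repair it. Sections 8 and 16 describe the data as anonymous, and the protocol provides no way back to the women to ask again.

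Two consequences follow. A real gradient could be missed or blunted, and a null result for education would be hard to interpret. Also, if few staff tick the lower box, most of the remaining contrast would come from patients and caregivers. In the pooled sample it could then overlap with recruitment route and survey mode.

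**Working it through.** The protocol has no sample-size, power or effect figure for education, so there is nothing to reproduce. The structural point needs no arithmetic: two categories give one contrast. The calculations below only size the loss.

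**1. Information kept by the present cut**

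Assume three levels scored 0 (middle school or less), 1 (diploma) and 2 (degree), with shares a, b and c, and a linear trend in the score. Question 7 records 0/1/1. The share of information kept is the squared correlation of the two codings. With mean m = b + 2c and variance V = b + 4c − m²:

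r² = m²·a / [V·(1 − a)]

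All shares are assumptions.

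| a/b/c | m | V | r² |
|---|---|---|---|
| 25/45/30% | 1.05 | 0.5475 | 1.1025 × 0.25 / (0.5475 × 0.75) = 0.67 |
| 15/45/40% | 1.25 | 0.4875 | 1.5625 × 0.15 / (0.4875 × 0.85) = 0.57 |
| 3/40/57% | 1.54 | 0.3084 | 2.3716 × 0.03 / (0.3084 × 0.97) = 0.24 |

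The third row is a deliberately extreme mix for staff. Mixes with more women in the lower box lose less: 40/45/15% gives 0.5625 × 0.40 / (0.4875 × 0.60) = 0.77. If UI changes only at the middle-school threshold, the present cut is the right coding and nothing is lost.

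**2. What the one remaining contrast could show among staff**

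Inputs: 1,842 staff (Section 11), taken as if all responded; UI of 25% in the upper box (lower end of the 25–45% range in Section 11); two-sided 5% test (assumed); share s in the lower box (assumed). Power is Φ[(d − 1.96·SE₀)/SE₁], where d is the difference, SE₀ the pooled and SE₁ the unpooled standard error.

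Worked case, s = 10% and d = 10 points: 184.2 women at 35% and 1,657.8 at 25%; pooled proportion 0.26; SE₀ = 0.0341; SE₁ = 0.0367; (0.10 − 0.0668)/0.0367 = 0.905; power 82%.

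| s | Women in lower box | Power for 10 points | Difference with 80% power |
|---|---|---|---|
| 1% | 18 | 19% | 29.8 points |
| 5% | 92 | 57% | 13.5 points |
| 10% | 184 | 82% | 9.8 points |
| 20% | 368 | 97% | 7.3 points |

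With half responding (921), the four powers are 13%, 34%, 54% and 77%.

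**3. What a separate degree box would allow**

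If UI were 35% with a diploma and 25% with a degree (assumed), and diploma holders made up 30–70% of those compared, power would be about 99% among 1,842 staff and 86–91% among 921. With the present item this contrast cannot be estimated at all.

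**The case against.** The strongest reply is that question 7 contradicts no stated analysis. The rising-level sentence in Table 1 summarises literature, Sections 4 and 5 promise only predictors and associations, and a two-level item can show an association. A reader might infer that the protocol commits to testing education as a graded predictor. It does not: Section 13 specifies no ordering or trend. What stands is a mismatch between the reason for collecting the variable and the way it is collected.

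A reader might also infer that the item will be nearly constant among hospital staff. That is plausible from the occupations named, but no staff education figures or entry qualifications are given. The second table shows how much depends on the unknown share: the loss is severe at 1–5% in the lower box and modest at 20% with full response. The 1,842 are also employees, not respondents, and some will meet the exclusion criteria in Section 7.2. Patients and caregivers may fill both boxes, so the item need not be sparse overall.

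Thirdly, a reader might conclude that the education effect is inevitably confounded with recruitment route. The documents support only a risk. Route is identifiable in principle, because staff enter data online and the others use numbered paper modules, so the contrast can be examined within route. Splitting the box would not remove an association between education and route either, since staff and patients may still differ in their share of degrees. It would add usable variation within staff.

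Finally, education is one of many predictors and serves a secondary outcome. That limits the weight of the point without answering it.

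**Conclusion.** The point holds as a measurement weakness. That question 7 is the only education item, has one cut-off and merges every upper-secondary diploma with the degree is certain from the text. So is the consequence that a gradient and a diploma-versus-degree contrast are out of reach.

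The size is conditional. Roughly one third to three quarters of the information on a linear trend is lost under the three main assumed mixes, and none if the effect is a threshold at middle school. Sparse lower-box counts among staff, and any overlap with recruitment route, are plausible but undocumented. The change is worth making before data collection because it cannot be made afterwards, but it does not threaten the study's main result.

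**What to change.** Replace the two boxes of question 7 with four:

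1. elementary school
2. middle school
3. upper-secondary or vocational diploma
4. university degree or higher

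In the predictor analysis, use the ordered levels, and examine the education association within recruitment route (staff; patients and caregivers) before pooling. Merging levels 1–2 and 3–4 restores the present coding, so comparability is kept.

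The cost is two extra tick boxes. Question 7 belongs to the survey written by the researchers, so neither validated questionnaire is touched. The form would differ slightly from the one piloted in 13 women (Section 9.1.1), where clarity, difficulty and completion time were checked; a brief recheck of this one item would cover that.

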The questionnaire comprises four question items and the reference period for symptom assessment is the four weeks preceding the day that the questionnaire is administered. The total score for the ICIQ-SF is calculated as the sum of scores obtained from the frequency of urinary incontinence episodes (from 0 or 'never', increasing by 1 unit up to 5 or 'always'), perceived quantity of urine losses (0 or 'no loss', increasing by 2 units up to 6 or 'a large amount') and quality of life (from 0 or 'no interference' of urinary incontinence with life, increasing by 1 unit up to 10 or 'maximum interference'). The theoretical range of total score values is therefore 0-21. A higher score indicates greater impairment from incontinence. The fourth question is an unscored self-diagnostic item about the type of urine leakage (Tubaro et al., 2006).

The instrument has a GRADE A on the level of validation according to the International Consultation of Incontinence (ICI) grades of recommendation; this means that the questionnaire has good validity, reliability and responsiveness established with rigor in several data sets. Specifically, the internal consistency of the ICIQ-SF is satisfactory overall, with a Cronbach's α of 0.896. Also the test-retest reliability is good; the Pearson r coefficient is almost equal to 1 for the total score and varies steadily at ≈ 0.9 for all items. Intraclass correlation coefficients for the total score and the quality of life item are, respectively, 0.93 and 0.96 (Tubaro et al., 2006). The entire questionnaire is attached in the Appendix (questions n. 24-27).

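### Question 8 cannot separate current from resolved conditions, or a woman with no condition from one who skipped the item

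*Protocol*

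**What the plan says.** The Appendix form asks in question 8 "Soffre o ha mai sofferto di una delle seguenti patologie" and allows several answers ("Può indicare anche più di una risposta"). The options are fourteen named conditions and a closing *Altro* with a write-in line. Each condition has one box. No date is asked, there is no current/past split, and no option means that none applies. The last named condition is printed as "14. Disabilità cognitiva generale", and *Altro* carries the number 14 as well.

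Table 1 (section 9) lists these conditions among the predictors of urinary incontinence (UI) with the rationale "Lower urinary tract symptoms are associated with multiple comorbid conditions including". Section 4 makes this a secondary outcome: "Association between UI and related predictors, quality of life, social impact and costs".

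UI itself is measured with the ICIQ UI-SF. Section 9.1.2 says that "the reference period for symptom assessment is the four weeks preceding the day that the questionnaire is administered", and the form repeats this ("nelle ULTIME QUATTRO SETTIMANE").

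Patients and caregivers complete the form on paper, and researchers enter it by hand. Staff complete it in RedCap (sections 8 and 16). Both streams are described as anonymous.

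**The concern.** Two pieces of information are lost when the form is filled in.

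- **Timing of the condition.** Depression, constipation, sleep disturbance or recurrent urinary infection that ended long ago is recorded in the same way as the condition present today. Only lifetime status can then be analysed. If a resolved condition matters less than a current one, the association for the current condition is diluted.
- **Meaning of a blank.** A healthy woman and a woman who passed over the item return the same empty list. Any rule for coding blanks has to guess between them.

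At stake are the description of comorbidity in women with UI and the comorbidity associations, both secondary. The prevalence of UI does not depend on question 8.

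**Working it through.** The protocol gives no figure on this point, so there is none to reproduce. The check has three steps.

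**1. Question 8 against other items on the same form**

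| Item | Separates current from past? | Explicit negative answer? |
|---|---|---|
| Question 8, conditions (tick all) | No | No |
| Question 18, smoking | Yes: current, former, never | Yes |
| Question 27, situations of leakage (tick all) | Not applicable | Yes: "Mai – non ho perdite di urina" |
| Questions 9 and 12, surgery and children | Not applicable | Yes: No |

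The form already uses both devices that question 8 lacks. The printed list runs to its closing *Altro*, so the missing option is unlikely to be a loss in text extraction.

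**2. Size of a dilution from merged timing**

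Assumptions, none of them given in the protocol for this purpose:
- UI risk in women who never had the condition: p0 = 0.30. This lies within the 25–45% that section 11 gives for most studies.
- True odds ratio (OR) for a current condition: 2.0.
- OR for a resolved condition: 1.0, 1.5 or 2.0.
- Share c of ticks that are current: 75%, 50% or 25%.

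Formulas:
- baseline odds o0 = 0.30/0.70 = 0.4286
- risk at a given OR = OR × o0 / (1 + OR × o0)
- risk among ticked women: p = c × p(current) + (1 − c) × p(past)
- observed OR = [p/(1 − p)] / o0

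Risks: p(current) = 0.8571/1.8571 = 0.4615. p(past) = 0.3000 at OR 1.0 and 0.6429/1.6429 = 0.3913 at OR 1.5.

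| Share current | p, past OR 1.0 | Observed OR | p, past OR 1.5 | Observed OR | Observed OR, past OR 2.0 |
|---|---|---|---|---|---|
| 75% | 0.4212 | 1.70 | 0.4440 | 1.86 | 2.00 |
| 50% | 0.3808 | 1.43 | 0.4264 | 1.73 | 2.00 |
| 25% | 0.3404 | 1.20 | 0.4089 | 1.61 | 2.00 |

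Example for 50% and past OR 1.5: p = 0.5 × 0.4615 + 0.5 × 0.3913 = 0.4264. The odds are 0.4264/0.5736 = 0.7434, and 0.7434/0.4286 = 1.73.

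**3. Size of the effect if blanks were read as no condition**

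Assumptions: no resolved conditions, UI risk without the condition 25% or 45%, condition present in 10% or 20% of women, true OR 2.0. Among women with the condition, 10% or 20% leave the item blank, regardless of UI.

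Example with risk 25%, condition 20%, skipping 20%:
- Ticked: 0.20 × 0.80 = 0.16, with UI risk 0.40 and odds 0.6667.
- Unticked: 0.84, with UI risk (0.80 × 0.25 + 0.04 × 0.40)/0.84 = 0.2571 and odds 0.3462.
- Observed OR = 0.6667/0.3462 = 1.93.

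Over all these combinations the observed OR lies between 1.98 and 1.93. The recorded frequency of the condition falls by 10–20% in relative terms, here from 20% to 16%. In this model skipping hardly moves the association and mainly lowers the recorded comorbidity.

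**The case against.** The strongest reply is that a lifetime question is legitimate. The survey introduction says it looks for factors that may predispose to the onset of UI, and question 35 allows leakage that began more than ten years ago. For such a woman the relevant exposure may lie well in the past. Surgery and parity are also asked as history. This stands: a reader might infer that a lifetime exposure set against a four-week outcome is an error in itself, and the documents do not support that. Four weeks is the window for ascertaining leakage, not the period in which its causes must have acted.

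A reader might also conclude that the associations will be diluted, or that only current conditions should be used as predictors. Neither follows. Dilution depends on past conditions having a weaker effect, on which the protocol says nothing. Current depression or sleep disturbance may have begun after the leakage, so a current-only predictor invites reverse causation.

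Nor does any section say that blanks will be counted as no comorbidity. Their coding may be set in the analysis plan or the RedCap build, which are not shown. What remains is that no coding rule can recover a distinction the form does not record. Making the item mandatory in RedCap would not help, because a healthy woman would have no true box to tick. Paper forms are handed back to researchers, who might notice a blank, but no such check is described. Section 16.1 mentions an identification number, yet section 16 says the data cannot be attributed to an individual, so no route for a later query is described. The pilot in 13 women (section 9.1.1) assessed clarity, difficulty and completion time; it does not report on either issue.

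The repeated number 14 is clerical. The two boxes have different labels, and nothing shows that the database stores the printed number.

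**Conclusion.** The point holds as a loss of information at collection. Question 8 supports an analysis of lifetime status only, and its blanks are ambiguous. The consequence is confined to the comorbidity part of the secondary outcomes. It bears mainly on conditions that can remit, and little on lifelong ones such as diabetes or chronic renal failure.

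The weakening of an OR of 2.0 ranges from none, when past and current effects are equal, to an observed 1.20, when past conditions have no effect and only a quarter of ticks are current. The baseline risk, the ORs and the share of current ticks are all assumptions. The ambiguity of blanks matters more for the described frequency of comorbidity than for the associations, and its size depends on a skipping rate that the protocol does not give. This is a modest improvement, worth making because it is cheap and cannot be made after collection.

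**What to change.** In question 8, on paper and in RedCap:

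- Add a box *nessuna di queste*, and code a wholly blank item as missing.
- Replace the single tick with two columns, *attualmente* and *solo in passato*, following the logic of question 18. The two together give ever status, so both current and lifetime status can be analysed. The form need not settle which is the predictor.
- Renumber *Altro* as 15, as a clerical tidy-up.

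The cost is an amended appendix, a new layout for one item in both versions and a little more completion time. The past-only category will be small for some conditions and its estimates imprecise.
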